7.2 Enrollment/Baseline

7.2.1. Baseline Assessment (Period 1: Study Assessment Day 1 through Study Assessment Day 3, unless broader window specified)

- Confirm that informed consent has been obtained from parent or legally authorized representative
- Document baseline demographics (see Section 8.1.1; Window: Birth through Study Assessment Day 3)
 - Gestational age at delivery
 - Date of birth
 - Day of life at initiation of IV ganciclovir therapy
 - Gender
 - Race
 - Ethnicity
 - Birth weight
 - Weight at enrollment
 - Length in centimeters at enrollment
 - Reason ganciclovir being administered
 - Ganciclovir dose and dosing frequency
 - Manufacturer of the ganciclovir lot utilized at the treating facility
 - Date ganciclovir therapy was initiated
- Hematology labs (see Section 8.2; Window: Birth through Study Assessment Day 3)
 - WBC with differential, hemoglobin, and platelet count, if being drawn for clinical reasons; any laboratory value obtained during the window will suffice, with an effort being made to capture the most abnormal value
- Chemistry labs (see Section 8.2; Window: Birth through Study Assessment Day 3)
 - AST and ALT, if being drawn for clinical reasons; any laboratory value obtained during the window will suffice, with an effort being made to capture the most abnormal value

- Serum Creatinine (see Section 8.2.)
 - To be drawn on the calendar day that ganciclovir PKs are being drawn (Window: Study Assessment Day 1 through Study Assessment Day 5)
 - Required amount of whole blood for serum creatinine is 0.25 mL
- Ganciclovir pharmacokinetics (see Section 8.2.2.2.)
 - Ganciclovir concentrations will be obtained with one of the Study Assessment Dose 3, 4, 5, 6, 7, or 8 (Window: Study Assessment Day 1 through Study Assessment Day 5)
 - Timepoints for pharmacokinetic draws: 0h (immediately prior to IV ganciclovir dose; window: -15 min), 1h (immediately after the end of the IV ganciclovir dose; window: +15 min), 2-3h, 5-7h, and 10-12h
 - Required amount of whole blood for plasma ganciclovir determination at each timepoint is 200 μ L (0.2 mL)
- Virology specimens (see Sections 8.2.2.1.)
 - Blood for CMV quantitative PCR will be obtained (required amount of whole blood for CMV PCR is 0.5 mL)
 - If obtainable, urine for CMV detection will be collected non-invasively (e.g., bagged, from indwelling foley catheter, excess clinical specimen, etc.)
- Clinical treatment ganciclovir dosing information
 - mg/dose
 - Dosing interval
 - Patient weight

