7.3.3. Period 4 (Study Assessment Day 18 through Study Assessment Day 24)

- Documentation of receipt of PRBC transfusion(s) will be provided on an eCRF. If the study subject has NOT received ≥ 10 PRBC transfusions (see Section 9.3.1), proceed with required assessments.
- Confirmation that subject is still receiving ganciclovir (e.g., that the ganciclovir has not been permanently discontinued)
- Hematology labs (see Section 8.2)
 - WBC with differential, hemoglobin, and platelet count, if being drawn for clinical reasons; any laboratory value obtained during the window will suffice, with an effort being made to capture the most abnormal value
- Chemistry labs (see Section 8.2)
 - AST and ALT, if being drawn for clinical reasons; any laboratory value obtained during the window will suffice, with an effort being made to capture the most abnormal value
- Serum creatinine (see Section 8.2)
 - Obtain if the ganciclovir pharmacokinetics are being obtained during this study assessment period

- To be drawn on the calendar day that ganciclovir PKs are being drawn
- Ganciclovir pharmacokinetics, if desired by the treating physicians and the subject weighs \geq 575 grams at that time (see Section 8.2.2.2.)
 - Ganciclovir concentrations may be obtained around one dose in this assessment window (Study Assessment Day 18 through Study Assessment Day 24)
 - Timepoints for pharmacokinetic draws: 0h (immediately prior to IV ganciclovir dose; window: -15 min), 1h (immediately after the end of the IV ganciclovir dose; window: +15 min), 2-3h, 5-7h, and 10-12h
 - Required amount of whole blood for plasma ganciclovir determination at each timepoint is 200 μ L (0.2 mL)
 - If subject weighs $<$ 575 grams, the second set of PK draws cannot be performed
- Virology specimens (see Sections 8.2.2.1.)
 - Blood for CMV quantitative PCR will be obtained (required amount of whole blood for CMV PCR is 0.5 mL)
 - If obtainable, urine for CMV detection will be obtained non-invasively (e.g., bagged, from indwelling foley catheter, excess clinical specimen, etc.)
- Ganciclovir dosing information
 - mg/dose
 - Dosing interval
 - Subject weight

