h) Ganciclovir concentrations will be obtained with one of the Study Assessment Doses 3, 4, 5, 6, 7, or 8 (Window: Study Assessment Day 1 through Study Assessment Day 5) at the following time points: 0h (immediately prior to IV ganciclovir dose; window: -15 min), 1h (immediately after the end of the IV ganciclovir dose; window: +15 min), 2-3h, 5-7h, and 10-12h; required amount of whole blood for plasma ganciclovir determination at each time point is 200 μ L (0.2 mL). Study related laboratory draws will be delayed or deferred if the investigator believes that obtaining them might increase subject risk. Additionally, a study-related laboratory specimen that is unevaluable due to clotting or laboratory related issues will not be repeated. If a study related laboratory draw is delayed or deferred, study staff will document this on a source document.

i) If desired by the treating physicians, ganciclovir concentrations may be obtained around one dose during the window at the following time points: 0h (immediately prior to IV ganciclovir dose; window: -15 min), 1h (immediately after the end of the IV ganciclovir dose; window: +15 min), 2-3h, 5-7h, and 10-12h; required amount of whole blood for plasma ganciclovir determination at each time point is 200 μ L (0.2 mL). Optional laboratory draws are not required by the protocol, and so no documentation on a source document will be required.

j) If subject weighs < 575 grams, the second set of PK draws cannot be performed (would exceed blood draw parameters of 7 mL/kg over 42 days)

k) To be obtained only once per study period; ideally, at least 72 hours should separate viral loads being obtained in different study periods

l) Required amount of whole blood for CMV PCR is 0.5 mL. Study related laboratory draws will be delayed or deferred if the investigator believes that obtaining them might increase subject risk. Additionally, a study-related laboratory specimen that is unevaluable due to clotting or laboratory related issues will not be repeated. If a study related laboratory draw is delayed or deferred, study staff will document this on a source document.

m) If subject weighs < 600 grams, the virology specimen for CMV viral load will not be performed (would exceed blood draw parameters of 7 mL/kg over 42 days)

n) If subject weighs < 650 grams, the virology specimen for CMV viral load will not be performed (would exceed blood draw parameters of 7 mL/kg over 42 days)

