- *Physical Security*: See **Appendix H**

8. *Other systems to be configured*

- a. *Tracking System*: All requests for modifications or additions to the DEMS are managed through the Tracking System. This application maintains an audit trail of request, development, validation, verification, and status of any modification or addition to the DEMS. The Tracking System Manual of Operations is available on request.
- b. *Database Interface for Laboratories*: Depending on the data requirements (real-time vs batch), laboratories will be provided with a data entry interface or a mechanism for uploading an Excel spreadsheet with results. Regardless of the mechanism for inclusion in the study database, all laboratory data will be checked in real time for adherence to pre-specified ranges as well as logic and consistency checks.

6. CRF Workflow

Table 1. Schematic of Study Design for 11-0067 (Gan Premie)

	Period 1(Study Assessment Days 1 - 3)	Period 2 (Study Assessment Days 4 - 10) ^a	Period 3 (Study Assessment Days 11- 17) ^a	Period 4 (Study Assessment Days 18 -24) ^a	Period 5 (Study Assessment Days 25 -31) ^a	Period 6 (Study Assessment Days 32 -38) ^a	Period 7 (Study Assessment Days 39 - 42) ^a	
Baseline demographics ^b	X ^c							
Hematology labs ^d	X ^{c,e}	X ^e						
Chemistry labs ^f	X ^{c,e}	X ^e						
Creatinine	X ^g	X ^e						
Ganciclovir pharmacokinetics	X ^h				X ^{i,j}			
Virology blood specimens for CMV viral load ^k	X ^l	X ^l	X ^l	X ^l	X ^l	X ^{l,m}	X ^{l,n}	
CMV detection from noninvasive urine specimen	X ^o	X ^o	X ^o	X ^o	X ^o	X ^o	X ^o	
Ganciclovir dosing information	X ^p	X ^p	X ^p	X ^p	X ^p	X ^p	X ^p	
PRBC transfusion assessment	X ^q	X ^q	X ^q	X ^q	X ^q	X ^q	X ^q	
Assessment for AEs or SAEs		X	X	X	X	X	X	
Total volume of blood required for study procedures	1.75 mL	0.5 mL	0.5 mL	0.5 mL or 1.5 mL ⁱ	0.5 mL	0.5 mL	0.5 mL	

- a) Data and specimens in this column to be captured if subject still receiving ganciclovir as clinical treatment
- b) Gestational age at delivery, date of birth, day of life at initiation of IV ganciclovir therapy, gender, race, ethnicity, birth weight, weight at enrollment, length in centimeters at enrollment, reason ganciclovir being administered, ganciclovir dose and dosing frequency, manufacturer of the ganciclovir lot utilized at the treating facility, date ganciclovir therapy was initiated
- c) Window: Birth through Study Assessment Day 3

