- d) WBC with differential, hemoglobin, platelet count. Optional laboratory draws are not required by the protocol, and so no documentation on a source document will be required.
- e) If being drawn for clinical reasons; any laboratory value obtained during the window will suffice, with an effort being made to capture the most abnormal value. Optional laboratory draws are not required by the protocol, and so no documentation on a source document will be required.
- f) AST, ALT. Optional laboratory draws are not required by the protocol, and so no documentation on a source document will be required.
- g) To be drawn on the calendar day that ganciclovir PKs are being drawn. Study related laboratory draws will be delayed or deferred if the investigator believes that obtaining them might increase subject risk. Additionally, a study-related laboratory specimen that is unevaluable due to clotting or laboratory related issues will not be repeated. If a study related laboratory draw is delayed or deferred, study staff will document this on a source document.
- h) Ganciclovir concentrations will be obtained with one of the Study Assessment Doses 3, 4, 5, 6, 7, or 8 (Window: Study Assessment Day 1 through Study Assessment Day 5) at the following time points: 0h (immediately prior to IV ganciclovir dose; window: -15 min), 1h (immediately after the end of the IV ganciclovir dose; window: +15 min), 2-3h, 5-7h, and 10-12h; required amount of whole blood for plasma ganciclovir determination at each time point is at least 200 μ L (0.2 mL). Study related laboratory draws will be delayed or deferred if the investigator believes that obtaining them might increase subject risk. Additionally, a study-related laboratory specimen that is unevaluable due to clotting or laboratory related issues will not be repeated. If a study related laboratory draw is delayed or deferred, study staff will document this on a source document.
- i) If desired by the treating physicians, ganciclovir concentrations may be obtained around one dose during the window at the following time points: 0h (immediately prior to IV ganciclovir dose; window: -15 min), 1h (immediately after the end of the IV ganciclovir dose; window: +15 min), 2-3h, 5-7h, and 10-12h; required amount of whole blood for plasma ganciclovir determination at each time point is at least 200 μ L (0.2 mL). Optional laboratory draws are not required by the protocol, and so no documentation on a source document will be required.

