- j) If subject weighs < 575 grams, the second set of PK draws cannot be performed (would exceed blood draw parameters of 7 mL/kg over 42 days)
- k) To be obtained only once per study period; ideally, at least 72 hours should separate viral loads being obtained in different study periods
- l) Required amount of whole blood for CMV PCR is at least 0.5 mL. Study related laboratory draws will be delayed or deferred if the investigator believes that obtaining them might increase subject risk. Additionally, a study-related laboratory specimen that is unevaluable due to clotting or laboratory related issues will not be repeated. If a study related laboratory draw is delayed or deferred, study staff will document this on a source document.
- m) If subject weighs < 600 grams, the virology specimen for CMV viral load will not be performed (would exceed blood draw parameters of 7 mL/kg over 42 days)
- n) If subject weighs < 650 grams, the virology specimen for CMV viral load will not be performed (would exceed blood draw parameters of 7 mL/kg over 42 days)
- o) Urine collection will be non-invasive (e.g., bagged, indwelling foley catheter, excess clinical specimen, etc.). If urine is obtainable, it will be frozen and sent to the UAB Central Laboratory for processing. If an attempt to obtain urine for CMV detection is unsuccessful, study staff will document the failed attempt on a source document.
- p) mg/dose, dosing interval, subject weight
- q) Once during each Study Period the study team will record the number of PRBC transfusions received by the study subject since enrollment (for the Period 1 documentation) or since the last recording (for documentation for Periods 2-7). A PRBC transfusion is defined as ≥ 10 mL/kg of PRBCs within a 24 hour period.

Within 3 days after the end of a study period, the user will enter data in the eDES from source documents (specific guidelines provided in the protocol specific MOP) collected at the time of the visit.

Systems Workflow

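### The SAP schedule turns the research blood volumes into minimums while keeping fixed totals and weight cut-offs tied to 7 mL/kg, and those cut-offs do not hold even at the protocol's single amounts once creatinine is counted

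*SAP*

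**What the plan says.** **PK draws.** Protocol Appendix A, footnotes h and i: "required amount of whole blood for plasma ganciclovir determination at each time point is 200" µL. The SAP copy of the table (section 6, CRF Workflow, Table 1), same footnotes: "required amount of whole blood for plasma ganciclovir determination at each time point is at least 200" µL.

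**CMV PCR draws.** Protocol Appendix A, footnote l: "Required amount of whole blood for CMV PCR is 0.5 mL". SAP Table 1, footnote l: "Required amount of whole blood for CMV PCR is at least 0.5 mL".

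Protocol Sections 7.2.1, 7.3.3, 8.2.1.1 and 8.2.1.2 repeat the single amounts where they mention these draws. The SAP footnotes give no maximum.

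**Totals and cut-offs.** In both documents the row "Total volume of blood required for study procedures" reads 1.75 mL for Period 1, 0.5 mL for each later period, and 1.5 mL for Period 4 if a second PK set is drawn. Both withhold the second PK set below 575 g, the Period 6 viral load below 600 g and the Period 7 viral load below 650 g. The reason given each time is that the draw "would exceed blood draw parameters of 7 mL/kg over 42 days". Entry requires at least 500 g (Protocol Section 5.1).

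**Creatinine.** Protocol Section 7.2.1: "Required amount of whole blood for serum creatinine is 0.25 mL", drawn on the PK day. For Period 4, Section 7.3.3 says of serum creatinine: "Obtain if the ganciclovir pharmacokinetics are being obtained during this study assessment period".

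**The concern.** The SAP table contradicts the protocol and also itself. A period total of 0.5 mL, or a cut-off derived from it, is valid only if 0.5 mL is what is drawn. If it is the least that may be drawn, the total is a lower bound and the cut-off no longer shows that 7 mL/kg is respected.

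This touches a stated safety limit. Protocol Section 9 confines study risk to the risks of blood draws, and Section 2.3.1 relies on the 500 g entry weight to keep the volumes acceptable. That assurance is only as good as the volume arithmetic behind it.

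**Working it through.** **Inputs.** PK set: 5 time points × 0.2 mL = 1.0 mL. CMV PCR: 0.5 mL once per period. Creatinine: 0.25 mL with the PK set. Limit: 7 mL/kg over 42 days. The documents do not say which weight is the denominator. I use the weight at the draw that the cut-off governs, and 500 g for an infant still at entry weight in Period 5.

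**Reproducing the volume row.** Period 1: 1.0 + 0.25 + 0.5 = 1.75 mL, as printed. Period 4 with a second PK set: 0.5 + 1.0 = 1.5 mL, as printed, but without creatinine. Adding the creatinine that Section 7.3.3 asks for gives 1.75 mL. The schedule table marks Period 4 creatinine as recorded only if drawn clinically, so the table and Section 7.3.3 also disagree.

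**Reproducing the cut-offs.** Minimum weight = cumulative volume ÷ 7 mL/kg. The creatinine column counts the Period 1 creatinine only, as the printed totals do.

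| Point in schedule | PK + PCR volume | Minimum weight without creatinine | Minimum weight with 0.25 mL creatinine | Stated weight |
|---|---|---|---|---|
| Period 5, no second PK set | 1.0 + 5 × 0.5 = 3.5 mL | 500 g | 3.75 ÷ 7 = 536 g | 500 g (entry) |
| Period 4, second PK set | 2.0 + 4 × 0.5 = 4.0 mL | 571 g | 4.25 ÷ 7 = 607 g | 575 g |
| Period 6, no second PK set | 1.0 + 6 × 0.5 = 4.0 mL | 571 g | 4.25 ÷ 7 = 607 g | 600 g |
| Period 7, no second PK set | 1.0 + 7 × 0.5 = 4.5 mL | 643 g | 4.75 ÷ 7 = 679 g | 650 g |

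The stated weights fit the limit only if creatinine is left out. The volume row does include it in Period 1.

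**Exposure at the stated weights.** mL/kg = volume ÷ weight. Slack without creatinine = (7 × weight ÷ volume) − 1. The overdraw applies to every PK and PCR draw; 10% is an assumption.

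| Weight | No creatinine | Slack | No creatinine, +10% | With creatinine | With creatinine, +10% |
|---|---|---|---|---|---|
| 500 g, Period 5 | 3.5 ÷ 0.500 = 7.00 | 0% | 7.70 | 3.75 ÷ 0.500 = 7.50 | 8.20 |
| 575 g, Period 4 with second PK set | 4.0 ÷ 0.575 = 6.96 | 0.6% | 7.65 | 4.25 ÷ 0.575 = 7.39 | 8.09 |
| 600 g, Period 6 | 4.0 ÷ 0.600 = 6.67 | 5.0% | 7.33 | 4.25 ÷ 0.600 = 7.08 | 7.75 |
| 650 g, Period 7 | 4.5 ÷ 0.650 = 6.92 | 1.1% | 7.62 | 4.75 ÷ 0.650 = 7.31 | 8.00 |

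For range, with creatinine and in the same row order, a 25% overdraw gives 9.25, 9.13, 8.75 and 9.04 mL/kg. A 50% overdraw gives 11.00, 10.87, 10.42 and 10.77.

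**Second PK set.** Counting a second 0.25 mL creatinine, the 575 g case becomes 4.50 ÷ 0.575 = 7.83 mL/kg. The Period 5 PCR has no weight cut-off. After a second PK set it brings the total, with one creatinine, to 4.75 mL, or 8.26 mL/kg if the infant is still at 575 g.

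**The case against.** The strongest reply is that the protocol governs what sites draw, and its amounts are unchanged. Protocol Section 15.6 defines a deviation against the protocol, GCP or the Manual of Procedures. The SAP, which is part of a data management plan, is not on that list. A reader might infer from the footnotes that a draw of any larger size complies and is not a deviation. The documents do not support that: it is true of the footnote wording alone.

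A reader might also infer that the SAP table drives the data checks, so that its wording is why an overdraw would go unnoticed. SAP Appendix C, item 4.2.2, compares the eCRFs with the protocol's schedule and narrative and with the Manual of Procedures. Nothing visible shows that drawn volume is captured or checked under either wording. The supportable statement is narrower: neither document states such a check.

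A third tempting reading is that the minimum wording is what leaves the limit unprotected and that the protocol amounts would protect it. The arithmetic shows otherwise once creatinine is counted. The protocol's required amount is also not called a maximum.

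Safeguards exist: discretionary deferral of draws (Protocol Section 5.3.2, repeated in footnotes g, h and l), no further study draws after 10 transfusions (Section 9.3.1), the enrollment halting rule (Section 9.3.2) and monthly transfusion reports (SAP section 11). None is tied to the volume drawn. The contradiction in wording and the arithmetic conflict both stand.

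**Conclusion.** The point holds as a minor one with a cheap correction. SAP footnotes h, i and l conflict with the protocol and with the fixed totals and cut-offs in the same table. The cut-offs have 0% to 5% slack with creatinine left out. With it counted, the printed volumes already exceed 7 mL/kg by 0.08 to 0.50 mL/kg at the stated weights. For infants without a second PK set the affected weight bands are narrow: 500 to 536 g through Period 5, 600 to 607 g at Period 6 and 650 to 679 g at Period 7. For the second PK set the band is 575 to 607 g.

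This rests on the weight at the draw as the denominator, on every scheduled draw being taken, and on research creatinine counting toward the limit, as its inclusion in the Period 1 total implies. The overdraw percentages are assumptions, and the documents give no evidence of how often overdraws occur. They do contain one unexplained tension: Protocol Section 8.2.1.2 describes the assay as using 200 µL of plasma, which 200 µL of whole blood cannot yield. The microspecimen method mentioned in Section 2.2 may resolve it.

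**What to change.** 1. Reconcile SAP Table 1 footnotes h, i and l with the protocol amounts.
2. State in both documents whether each amount is a minimum or a maximum, after checking the PK amount against the plasma volume in Protocol Section 8.2.1.2.
3. Recompute the volume row and the weight cut-offs in both documents against 7 mL/kg with creatinine included, including Period 4 and the draws that follow a second PK set. State which weight is the denominator.
4. Resolve the difference between Protocol Section 7.3.3 and the schedule table on Period 4 creatinine.

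No particular volume or cut-off is proposed here; that is for the sponsor and the investigators. The cost is a few words in the footnotes, a short recalculation, and a matching protocol amendment if the totals or cut-offs change. A check of cumulative drawn volume against 7 mL/kg could be added, but would need drawn volume to be recorded.

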APPENDIX B

DATA ANALYSIS PLAN

Study Hypotheses

Our primary hypothesis is that ganciclovir pharmacokinetics and pharmacodynamics in premature infants with postnatally or congenitally acquired CMV infection differ from those in term neonates and older infants.

Sample Size Considerations

The primary outcome used for power analysis is the area under the curve for 12 hours (AUC12) following 6 mg/kg of ganciclovir. In a one-way ANOVA design, we would like to compare the means of 4 groups with sample sizes of 8, 8, 8, and 8. If the means of the AUC12 of the 4 groups are 20, 20, 30, and 35 assuming a common standard deviation of 10, these mean differences (equivalent to an effect size of 0.72) will be detected at 83% power using an F test with 0.05 level of significance. In order to look at other possible scenarios, we provide the table below that looks at other standard deviation values, its corresponding effect size given the differences in means as described above, and the power of detecting such a difference/effect size.

Standard Deviation	S=8	S=9	S=10	S=11
Effect Size	0.81	0.72	0.64	0.59
Power	96%	91%	83%	75%

The above parameter values were hypothesized based on results from other studies.^{25,34} It is worth noting that there are no PK data in this population and the results are likely to be different from other studies due to the maturational changes.

Subjects will be stratified by gestational age and by chronologic age as follows: 1) \leq 27 weeks 6 days gestational age at birth and \leq 30 days chronologic age at study enrollment; 2) \leq 27 weeks 6 days gestational age at birth and $>$ 30 days chronologic age at study enrollment; 3) \geq 28 weeks 0 days gestational age at birth and \leq 30 days chronologic age at study enrollment; 4) \geq 28 weeks 0 days gestational age at birth and $>$ 30 days chronologic age at study enrollment.

Data will be collected on standardized case report forms. Standard non-compartmental techniques will be used initially to estimate pharmacokinetic parameters derived from the ganciclovir concentration-time data. The resource utilized for pharmacokinetic analysis is WinNonlin version 5.3, Pharsight Corporation, Mountain View, CA.

Planned Interim Analyses

There are no planned interim analyses or safety reviews for this trial.

Final Analysis Plan

Primary analysis: To compare the ganciclovir pharmacokinetics and pharmacodynamics as measured by AUC12 in premature infants with postnatally or congenitally acquired CMV infection differ from those in term neonates and older infants, we will utilize mixed models for repeated measures. Additional pharmacokinetic parameters that compose analyses for secondary endpoints include Cmax, T1/2, CL, and VD. In addition to being able to compare these outcomes

for the different groups, we can also look into how these measures change over time and adjust for covariates.

Ganciclovir pharmacokinetic parameters will initially be determined using non-compartmental analysis (WinNonlin v5.3) for each individual subject. The parameters (AUC₁₂, CL, Vd, etc.) will be summarized and further used for exploratory pharmacodynamic analysis. We will also apply pharmacokinetic models to the concentration-time data, either individually or using a population approach. We may also pool these data with prior CASG 109 PK data in order to have a more robust covariate analysis across a wider range of ages.

The second pharmacokinetic analysis will utilize either population pharmacokinetic or individual modeling approaches, depending upon how much data we actually are able to collect and the nature of those data. Concentration-time data will be analyzed using nonlinear mixed-effects in ADAPT 5.0. If a population approach is employed, this will give us the opportunity to explore relationships between ganciclovir exposure and multiple covariates, such as gestational age, weight, renal function, etc.

A 95% confidence interval will be constructed to evaluate the mean changes in the log of the viral load between baseline (day 1) and weeks 1, 2, 3, 4, 5, and 6. Area under the curve will be calculated for each subject's CMV viral load measurement utilizing the trapezoidal rule. These AUCs will be calculated over the entire course of drug administration. Spearman's correlations will be given for each AUC estimation and also for the AUC after baseline viral load (VL) adjustment. Analysis of variance will be used to investigate whether grouping AUCs into groups (undetected, 100-1000, 1000-10000 and ≥ 10000) would indicate any PD relationships. In addition, changes in CMV viral load from baseline over time (weeks 1 through 6) will be correlated with PK parameters. These data will provide the framework for all PD analyses, where ganciclovir exposures variables will be correlated with the response variables using linear or maximum effect PD models.

Secondary analyses: To investigate the association of secondary outcomes namely, neutropenia, CMV in urine, viral load and resistance to ganciclovir, with plasma concentration, we will utilize inference methods based on Generalized Estimating Equations (GEE) which models repeated binary data. As in the primary analysis, GEE will enable us to compare groups, investigate changes of outcomes over time, and adjust for any covariates.

